## **9.2 Safety Endpoints**

Safety measurements are described in section 7

## **9.3 Responsibility for Analyses**

The statistical data obtained from this study will be the responsibility of [name] and the clinical biostatisticians in the UCLA Department of Medicine Medical Statistics Core.

## **9.4 Hypothesis / Estimation**

Objectives and hypotheses of the study are stated in Section 3.0. The study is considered positive and to have met its primary efficacy endpoint if anti-tumor response rate of pembrolizumab meets or exceeds 26% (see sample size and power explanation below). The null hypothesis is derived from subpopulation data describing response rate in EGFR mutation positive NSCLC treated with TKI prior to single-agent pembrolizumab on KEYNOTE-001 study which is <8% in this population (36). Our study conservatively sets the null hypothesis at 10% objective response rate.

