### 3.0 OBJECTIVE(S) & HYPOTHESIS(ES)

#### 3.1 Primary Objective(s) & Hypothesis(es)

- (1) **Objective:** Determine efficacy [objective response rate (ORR)] of front-line pembrolizumab for Stage IIIB or IV metastatic EGFR mutation positive PD-L1+ (> 1% by IHC) NSCLC

**Hypothesis:** We hypothesize that over 26% of patients with Stage IIIB or IV EGFR mutation positive, EGFR TKI-naïve, PD-L1+ NSCLC will show a response with pembrolizumab.

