## **9.0 STATISTICAL ANALYSIS PLAN**

### **9.1 Efficacy Endpoints**

#### *Primary*

The primary efficacy analyses will be based on the Full Analysis Set (FAS). Patients with measurable disease at baseline who received at least one dose of study treatment will be included in the FAS. The primary efficacy endpoint is objective response rate (ORR) and will be determined by blinded central review. We will use an exact binomial test to evaluate the response rate to the null hypothesis value of 0.10.

Response duration is defined as the time from first documented evidence of response until progression, according to RECIST 1.1. Objective response rate is determined as the proportion of patients achieving complete response (CR) or partial response (PR) as respectively defined in RECIST 1.1. A 95% confidence interval will be provided for the objective response rate of the population. All patients

receiving at least one dose of pembrolizumab will be considered evaluable for efficacy and toxicity.

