## 9.6 Sample Size and Power Calculations

With 25 TKI-naïve patients treated at 200mg q3w, an exact binomial test with a nominal 0.10 one-sided significance level will have 81% power to detect the difference between the Null hypothesis response rate of 10% and the Alternative hypothesis rate of 26%.

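### The 26% success rule in 9.4 is not the exact test powered in 9.6: the test rejects at 5 of 25, and under the 26% rule power is 49%, not 81%

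*Combined protocol and SAP*

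**What the plan says.** Three parts of the combined protocol and SAP bear on the primary decision.

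- **Section 9.4 (Hypothesis / Estimation)** sets the success criterion: "The study is considered positive and to have met its primary efficacy endpoint if anti-tumor response rate of pembrolizumab meets or exceeds 26" per cent. It points to the sample size section for the explanation. It also fixes the null: "Our study conservatively sets the null hypothesis at 10% objective response rate".
- **Section 9.1 (Efficacy Endpoints, Primary)** names the analysis: "We will use an exact binomial test to evaluate the response rate to the null hypothesis value of 0.10". It adds that "A 95% confidence interval will be provided for the objective response rate of the population".
- **Section 9.6 (Sample Size and Power Calculations)** states that, with 25 patients, "an exact binomial test with a nominal 0.10 one-sided significance level will have 81% power". The two rates compared are "the Null hypothesis response rate of 10% and the Alternative hypothesis rate of 26" per cent.

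Section 3.1 words the primary hypothesis with the same figure: "We hypothesize that over 26% of patients". No section gives the number of responders at which the test rejects, or says which criterion decides if the test and the 26% rule disagree.

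**The concern.** In 9.6, 26% is the true response rate assumed under the alternative. In 9.4 the same 26% is the rate that must be observed. These are different quantities. If the observed bar sits close to the assumed true rate, a drug that performs exactly as hoped clears it only about half the time.

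The plan therefore holds two criteria that part company at 5 or 6 responders: the test rejects 10%, while 9.4 says the primary endpoint was not met. Response rate is the primary endpoint of a single-arm, open-label trial, so this is its main conclusion. If the count falls there, either verdict could be argued from the text after the data are seen. If 9.4 governs, the trial has far less power than a reader of 9.6 would believe.

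**Working it through.** **Inputs.** n = 25, null rate 0.10, alternative rate 0.26, one-sided level 0.10 and stated power 81% (9.6); exact binomial test against 0.10 (9.1); success if the observed rate is at least 26% (9.4).

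**Formula.** For a rule that declares success at r or more responders, with X ~ Binomial(25, p): alpha = P(X ≥ r | p = 0.10) and power = P(X ≥ r | p = 0.26).

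**Step 1: turn each criterion into a count.**
- 26% rule: 0.26 × 25 = 6.5. Six responders (24%) fail and seven (28%) pass, so r = 7.
- Exact test: r is the smallest count whose tail probability at p = 0.10 is no more than 0.10. P(X ≥ 4 | 0.10) = 0.2364 is too large; P(X ≥ 5 | 0.10) = 0.0980 qualifies. So r = 5 (20%).

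**Step 2: operating characteristics.**

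| Responders needed | Observed rate | Alpha at 10% | Power at 26% |
|---|---|---|---|
| ≥ 4 | 16% | 0.2364 | 0.9211 |
| ≥ 5 (exact test, 9.1 and 9.6) | 20% | 0.0980 | 0.8174 |
| ≥ 6 | 24% | 0.0334 | 0.6644 |
| ≥ 7 (26% rule, 9.4) | 28% | 0.0095 | 0.4851 |

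The r = 5 row reproduces the plan's 81% to within one point. No other row does, so 9.6 was calculated for a cut-off of 5 of 25.

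**Step 3: probability that the criteria disagree.** They disagree when X is 5 or 6.
- True rate 26%: 0.8174 − 0.4851 = 0.332.
- True rate 10%: 0.0980 − 0.0095 = 0.089 (0.0885 before rounding).

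**Step 4: true rate needed for 80% power under the 26% rule.** P(X ≥ 7 | 0.34) = 0.799, so a true response rate of about 34% is needed.

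**Step 5: does the result depend on n being exactly 25?** Section 1.0 says approximately 25, and Section 5.7 does not replace subjects who discontinue.

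| n | Test cut-off | Power of test at 26% | 26% rule cut-off | Power of 26% rule at 26% |
|---|---|---|---|---|
| 20 | 5 (25.0%) | 0.625 | 6 | 0.423 |
| 21 | 5 (23.8%) | 0.671 | 6 | 0.476 |
| 22 | 5 (22.7%) | 0.714 | 6 | 0.527 |
| 23 | 5 (21.7%) | 0.752 | 6 | 0.575 |
| 24 | 5 (20.8%) | 0.787 | 7 | 0.437 |
| 25 | 5 (20.0%) | 0.817 | 7 | 0.485 |
| 26 | 6 (23.1%) | 0.704 | 7 | 0.532 |
| 27 | 6 (22.2%) | 0.741 | 8 | 0.404 |
| 28 | 6 (21.4%) | 0.774 | 8 | 0.449 |

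At every n from 20 to 28 the test rejects below 26%, and the 26% rule has 40% to 58% power.

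**Step 6: the confidence interval.** The exact (Clopper-Pearson) 95% interval has lower limit 6.8% at 5 of 25 and 9.4% at 6 of 25. It includes 10% at both counts, although the one-sided 0.10 test rejects. The exact two-sided 80% interval leaves 10% in each tail and so matches the test: its lower limit is 10.06% at 5 of 25 and 13.1% at 6 of 25.

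**The case against.** The best defence is that only 9.4 says when the study is positive. Section 9.1 names a test and 9.6 gives that test's power; neither says that rejection makes the study a success. On that reading 5 or 6 responders has a defined meaning: null rejected, endpoint not met. The rules are nested, since 7 or more responders also rejects 10%, and requiring significance plus a higher observed rate is a legitimate design. The 81% and the nominal 0.10 are correct for the test they describe, and a stricter bar cannot inflate the false-positive rate.

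Much of this stands. The plan has two stated criteria that disagree, rather than none; no sum in 9.6 is wrong; the harm is to power and clarity, not to type I error. But the defence does not remove the fault. The documents never describe a dual criterion, and 9.4 cites the power section as its support, where the 81% belongs to a 20% cut-off. If a dual criterion was meant, 9.6 gives the wrong power for it.

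A milder reading takes the 26% in 9.4 as a loose reference to the design target. That may be how it arose, but Section 3.1 already states the target as a hypothesis, and 9.4 goes further by saying when the endpoint is met.

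Two smaller objections are fair. The 49% is specific to n = 25, although the shortfall is not. And a 95% interval beside a one-sided 0.10 test is not an error, because 9.1 gives the interval no role in the decision.

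**Conclusion.** The concern holds. The rule in 9.4 and the test in 9.1 and 9.6 are different decision rules, and the stated power belongs only to the test. At n = 25 the 26% rule has 48.5% power at the design alternative and 0.95% one-sided alpha, against 81.7% and 9.8% for the test. If the true rate is 26%, there is a one-in-three chance (0.332) of a count on which the two disagree.

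These figures assume 25 patients in the Full Analysis Set and independent responses with a common probability. The conflict itself persists at every n from 20 to 28. Because it decides the primary conclusion, it must be settled. The confidence interval point is secondary and the verdict does not rest on it.

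**What to change.** State one criterion in 9.4 and make 9.6 describe that criterion.

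- **Option A, which keeps the 81%.** Replace the 26% rule in 9.4 with: the study is positive if the exact one-sided binomial test against 10% gives p ≤ 0.10, that is, at least 5 responders among 25 Full Analysis Set patients. The cut-off is also 5 for any set of 20 to 24 patients and becomes 6 for 26 to 28, so define the rule by the p-value and give the count as its illustration. Keep 26% as the design alternative only.
- **Option B, if the sponsor wants the 26% bar.** Keep 9.4, say that at least 7 of 25 responders are needed, and restate 9.6 as about 49% power at 26% and 0.9% one-sided alpha.

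Optionally, add to 9.1 the exact two-sided 80% interval beside the 95% one, so that the reported interval agrees with the test.

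The cost is wording in 9.4 and either 9.1 or 9.6, with no added patients or data. Option A does lower the observed bar from 7 to 5 responders in an open-label trial already at Version 4, and the documents do not give accrual status. The choice should therefore be made without reference to response data, with the date and reason recorded.

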## **9.5 PD-L1 Biomarker**

Pearson correlation will evaluate correlation between PD-L1 expression in tumor samples and percent decrease in tumor volume following therapy. When the sample size is 25, the linear regression test for the Pearson correlation will have 80% power to detect a correlation of at least 0.51 assuming a two-side 0.05 level of significance.

We will evaluate the relationship between PD-L1 expression at baseline with clinical outcomes using regression models. For PFS and OS we will use Cox-proportional hazards regression.

A futility analysis will be conducted after nine patients with  $\leq 50\%$  PD-L1 expression (i.e. 1-49%) reach their first set of scans. If all nine patients have failed to respond to therapy, we will revise the protocol to restrict the study population to patients with PD-L1 staining of  $>50\%$ . Based on data to date, a response rate that low would not be anticipated for patients with  $>50\%$  PD-L1 expression.

## 9.6 Sample Size and Power Calculations

With 25 TKI-naïve patients treated at 200mg q3w, an exact binomial test with a nominal 0.10 one-sided significance level will have 81% power to detect the difference between the Null hypothesis response rate of 10% and the Alternative hypothesis rate of 26%.

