**EudraCT NUMBER (Studies in Europe only):**

**NCT Number: NCT02879994**

**Version 4      01 December 2017**

## 1.0 TRIAL SUMMARY

Abbreviated Title	Pembrolizumab in Frontline EGFR mutant, TKI-naïve NSCLC
Trial Phase	Phase II
Clinical Indication	The treatment of subjects with non-small cell lung cancer (NSCLC) whose tumors are positive for PD-L1 and harbor an EGFR mutation who have not been previously treated with an EGFR TKI
Trial Type	Interventional
Type of control	Active control without placebo
Route of administration	Intravenous
Trial Blinding	Unblinded Open-label
Treatment Groups	Pembrolizumab 200 mg every three weeks
Number of trial subjects	Approximately 25 patients will be enrolled.
Estimated enrollment period	We estimate that the trial will require approximately 16 months from the time the first subject signs the informed consent until the last subject's consent.
Estimated duration of trial	We estimate that the trial will require approximately 28 months from the time the first subject signs the informed consent until the subject's last visit.
Duration of Participation	Each subject will participate in the trial from the time the subject signs the Informed Consent Form (ICF) through the final protocol-specified contact. After a screening phase of up to 28 days, eligible subjects will receive assigned treatment on Day 1 of the 3-week (Q3W) dosing cycle. Treatment with pembrolizumab will continue until radiographic progression, documented disease progression, unacceptable adverse event(s), intercurrent illness that prevents further administration of treatment, investigator's decision to withdraw the subject, subject withdraws consent, pregnancy of the subject, noncompliance with trial treatment or procedure requirements, or administrative reasons. After progression on pembrolizumab, patients will be asked to undergo an additional biopsy and blood draw and be followed through periodic follow-up visits and calls (every 60 days) for evaluation of duration of response with the EGFR TKI as well as survival follow up
Estimated average length of treatment per patient	6 months

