### **5.7 Subject Replacement Strategy**

A subject that discontinues from the trial will not be replaced.

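### The 81% power in 9.6 is correct for 25 analysed patients, but 25 is the last size before the exact-test boundary steps up, and the plan does not hold the primary analysis at 25

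*Combined protocol and SAP*

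**What the plan says.** Section 9.6 gives one power figure for the primary endpoint. It is conditional on size ("With 25 TKI-naïve patients treated at 200mg q3w"), names the test and level ("an exact binomial test with a nominal 0.10 one-sided significance level will have 81% power"), and sets the hypotheses as "Null hypothesis response rate of 10% and the Alternative hypothesis rate of 26" percent. It gives no responder boundary, no attained alpha and no power at any other size.

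Section 9.1 names the same test: "We will use an exact binomial test to evaluate the response rate to the null hypothesis value of 0.10". Its denominator is the FAS: "Patients with measurable disease at baseline who received at least one dose of study treatment will be included in the FAS". The same section later counts every dosed patient as evaluable for efficacy, without repeating the measurable-disease condition.

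The enrolment target is looser than the power statement. Section 1.0 says "Approximately 25 patients will be enrolled", and section 2.1 repeats the approximate figure. No section says how accrual closes or how a 26th dosed patient would be analysed. Screening may last up to 28 days (section 1.0), and the trial is open-label (section 5.2.3).

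Section 9.4 gives a different criterion for success: "The study is considered positive and to have met its primary efficacy endpoint if anti-tumor response rate of pembrolizumab meets or exceeds 26" percent.

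**The concern.** The power of an exact binomial test does not rise smoothly with sample size. The responder boundary is a whole number. Power climbs while the boundary holds and drops when the boundary moves up by one. A plan that sits just below such a step and fixes its size only approximately can lose power by recruiting one patient too many.

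Two things are at stake. First, the only power stated for the primary test may not apply to the trial that is run. Second, the result can depend on the denominator: five responders among 25 reject the null and five among 26 do not, so one late non-responder reverses the primary test. If the plan is silent, the choice between 25 and 26 could be made after responses are known.

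**Working it through.** **Inputs.** Null rate 0.10, alternative 0.26, one-sided nominal alpha 0.10, exact binomial test, n=25 (9.6; test and null repeated in 9.1).

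**Rule.** For each n, the boundary r is the smallest count with P(X ≥ r | n, 0.10) ≤ 0.10. Power is P(X ≥ r | n, 0.26).

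**Reproducing the plan's figure, n=25, r=5.**
- Under 10%, the probabilities of 0 to 4 responders are 0.0718, 0.1994, 0.2659, 0.2265 and 0.1384, total 0.9020. Attained alpha is 1 − 0.9020 = 0.0980, within 0.10.
- Under 26%, the probability of 4 or fewer is 0.1826. Power is 1 − 0.1826 = 0.8174, which agrees with the stated 81%.
- At one-sided 0.05 the boundary would be 6 and power 66.4%. The stated one-sided 0.10 is therefore the level behind the 81%.

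**One more patient, n=26.**
- P(X ≥ 5 | 26, 0.10) = 0.1118, above 0.10, so 5 responders no longer reject.
- P(X ≥ 6 | 26, 0.10) = 0.0399, so the boundary is 6.
- P(X ≥ 6 | 26, 0.26) = 0.7042. The loss against n=25 is 81.7 − 70.4 = 11.3 percentage points.
- Keeping 5 as the boundary would give 84.4% power, but at alpha 0.112, above the nominal level.

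**Neighbouring sizes.**

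| FAS size | Boundary | Exact alpha | Power at 26% |
|---|---|---|---|
| 22 | 5 | 0.062 | 71.4% |
| 23 | 5 | 0.073 | 75.2% |
| 24 | 5 | 0.085 | 78.7% |
| **25** | **5** | **0.098** | **81.7%** |
| 26 | 6 | 0.040 | 70.4% |
| 27 | 6 | 0.047 | 74.1% |
| 28 | 6 | 0.055 | 77.4% |
| 29 | 6 | 0.064 | 80.4% |
| 30 | 6 | 0.073 | 83.0% |
| 32 | 6 | 0.094 | 87.5% |

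**The rule in 9.4.** An observed rate of at least 26% needs 0.26 × 25 = 6.5, so 7 of 25. Its exact alpha is 0.0095 and its power at 26% is 48.5%. At n=26, 0.26 × 26 = 6.76, again 7, with power 53.2%. The 81% in 9.6 belongs to the rule of at least 5 of 25, not to this one.

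**The case against.** The strongest reply is that 9.6 contains no error: it names 25 treated patients, and for 25 the figure is right. That stands. A reader might infer from the table that the stated power is wrong; the documents do not support that.

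A reader might also infer that 81% is attainable at no other size. That is too strong. Power is 80.4% at 29 and 83.0% to 87.5% from 30 to 32. The statement holds for 22 to 28, taken here as a fair range for an approximate target of 25.

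A third tempting reading blames section 5.7 ("A subject that discontinues from the trial will not be replaced"). It does not carry the point. A patient who stops after one dose remains in the FAS, and measurable disease is already an entry criterion (5.1.2, item 4), so dropout after dosing does not shrink the denominator. Nor can a ban on replacement cause over-enrolment, which is the only route to 70%. Only a patient enrolled and never dosed could reduce the count, and 5.7 does not clearly address that case.

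It is also fair to say that such steps occur in any small exact test, that the test at 26 is more conservative rather than invalid, that the response-rate estimate and its 95% interval are unaffected, and that nothing in the documents shows how likely over-enrolment is. Under the 9.4 rule alone, a 26th patient raises the chance of success from 48.5% to 53.2%. These points limit the severity. They do not remove the gap, because 9.1 and 9.6 still name the exact test and neither fixes its denominator.

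**Conclusion.** The point holds as a gap in how the sample size is specified, not as an arithmetic fault. The 81% is correct at 25. The design does not secure it: a shortfall of one costs about 3 points (78.7%), and an excess of one costs about 11 (70.4%). Type I error remains below 0.10 at every size tabulated. This rests on the exact test at one-sided 0.10 being the operative primary rule, as 9.1 and 9.6 say, and on reading the approximate target as 22 to 28.

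The conflict with 9.4 is larger than the loss from one extra patient and has to be settled alongside it. If 7 of 25 is the true criterion, the 81% does not describe the chance of a positive study at any denominator considered here.

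**What to change.** - **1.0, 2.1 and 9.6:** set the primary-analysis size at 25 FAS patients and close enrolment accordingly, so that a patient who is never dosed does not count towards the 25.
- **9.1:** pre-specify that if more than 25 are dosed, the primary exact test uses the first 25 FAS patients by first-dose date. Report the response rate and its 95% interval in all treated patients as well.
- **9.6:** state the boundary (at least 5 of 25, exact alpha 0.098) and the actual power if the FAS falls short: 78.7% at 24, 75.2% at 23, 71.4% at 22.
- **9.4:** reconcile the 26% success criterion with that boundary, so that one rule defines a positive study and the quoted power belongs to it.

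The cost is wording in the protocol and SAP, with no added visit or assessment. The real drawback is that a patient still in screening when the 25th is dosed is either not dosed or contributes only to the supportive analysis. Printing boundary and power for neighbouring sizes would be a lighter alternative. It would make the boundary clear but would not secure the stated power.

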## 10.0 LABELING, PACKAGING, STORAGE AND RETURN OF CLINICAL SUPPLIES

### 10.1 Investigational Product

The investigator shall take responsibility for and shall take all steps to maintain appropriate records and ensure appropriate supply, storage, handling, distribution and usage of investigational product in accordance with the protocol and any applicable laws and regulations.

Clinical Supplies will be provided by Merck as summarized in Table 7.

Table 7 Product Descriptions

Product Name & Potency	Dosage Form
Pembrolizumab 50 mg	Lyophilized Powder for Injection
Pembrolizumab 100 mg/ 4mL	Solution for Injection

### 10.2 Packaging and Labeling Information

Clinical supplies will be affixed with a clinical label in accordance with regulatory requirements.

### 10.3 Clinical Supplies Disclosure

This trial is open-label; therefore, the subject, the trial site personnel and/or designee are not blinded to treatment. Drug identity (name, strength) is included in the label text; random code/disclosure envelopes or lists are not provided.

### 10.4 Storage and Handling Requirements

Clinical supplies must be stored in a secure, limited-access location under the storage conditions specified on the label.

Receipt and dispensing of trial medication must be recorded by an authorized person at the trial site.

Clinical supplies may not be used for any purpose other than that stated in the protocol.

## **10.5 Returns and Reconciliation**

The investigator is responsible for keeping accurate records of the clinical supplies received from Merck or designee, the amount dispensed to and returned by the subjects and the amount remaining at the conclusion of the trial.

Upon completion or termination of the study, all unused and/or partially used investigational product will be destroyed at the site per institutional policy. It is the Investigator's responsibility to arrange for disposal of all empty containers, provided that procedures for proper disposal have been established according to applicable federal, state, local and institutional guidelines and procedures, and provided that appropriate records of disposal are kept.

